9.2.4 Safety Analyses

The safety evaluation will be based on the All Treated Population and the DLT evaluation will be based on the DLT evaluable population. DLTs will be summarized by dose level. Frequency tables will be used to describe safety and tolerability parameters AEs, irAEs, SAEs, fatal SAEs and AEs leading to discontinuation of SL-172154. Changes in toxicity grade for clinical chemistry and hematology will be summarized. Change from baseline QTcF will also be summarized. Graphs may also be presented where appropriate. AEs will be mapped to a Medical Dictionary for Regulatory Activities (MedDRA) preferred term and system organ classification. Laboratory abnormalities will be graded according to the NCI CTCTAE v5., if applicable. Concomitant medications will be coded using the World Health Organization Drug Dictionary.

MTD: The MTD will be estimated using isotonic regression (based on the DLTs observed in DLT evaluable subjects). Specifically, the MTD is the dose for which the isotonic estimate of the DLT rate is closest to the target DLT rate of 30%. If two or more doses tie for the smallest difference, perform the following rules:

- If the estimated DLT rate < 30% for all doses, then select the higher dose among the tied doses;
- If the estimated DLT rate for the tied doses are a combination of < 30% for and > 30%, then select the higher dose among the tied doses;
- If the estimated DLT rate > 30% for all dose, then select the lower dose among the tied doses.

A MAD will be reported if the observed DLT rate is <25% among all dose levels. Otherwise, an MTD will be reported.

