3.2 Statistical Design for Dose Escalation

The dose escalation will utilize a mTPI-2 design with target DLT rate of 30% for the MTD. The mTPI-2 design employs a simple Beta-Binomial Bayesian model with decision rules based on the unit probability mass from the posterior probability of DLT rate. With the target DLT rate of 30%, the posterior probability of DLT rate unit interval (0, 1) is divided into subintervals with equal length of 0.1 that correspond to different dose escalation decisions: subinterval of (0.25, 0.35) is to stay at the current dose, subintervals below 0.25 is to escalate to next higher dose, and subintervals above 0.35 is to de-escalate to the next lower dose. Subjects will be enrolled in cohorts of approximately 3 subjects during the dose escalation. After each cohort of approximately 3 subjects, the posterior unit probability for subintervals will be calculated based on a noninformative prior distribution for the DLT rate (Beta(1,1)) and the total number of subjects with DLTs and DLT evaluable subjects for the current dose. A dose escalation/stay/de-escalation decision that corresponds to the subinterval with the highest unit probability mass will be selected. A minimum of 3 DLT evaluable subjects will be enrolled to a dose level and evaluated for DLT before a dose escalation/stay/de-escalation decision can be made unless unacceptable toxicity is observed prior to the enrollment of 3 subjects e.g., two subjects experience DLT before the third subject enrolls. A dose level will be considered unsafe, with unacceptable toxicity and no additional subjects enrolled at that dose level and above, if it has an estimated 95% or greater probability of exceeding the target DLT rate of 30%. The maximum number of subjects evaluated for DLT for each dose level will be 12 subjects (about 4 cohorts of 3 subjects) if the dose escalation decision is to stay at the current dose from the first 3 cohorts.

Based on the above design, the dose escalation decision rules are as the following for each dose level:

- When the number of DLT evaluable subject is <12 subjects:
 - Dose escalate if the observed DLT rate <25%;

- Stay at the current dose if the observed DLT rate between 25%-33%;
- Dose de-escalate if the observed DLT rate $>33\%$;
- After reaching the maximum 12 subjects, the dose escalation decision will be either escalate or de-escalate as follows:
 - Dose escalate if the observed DLT rate $\leq 25\%$;

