8.1 Maximum Tolerated Dose Evaluation

The Maximum Tolerated Dose (MTD) evaluation will be based on the DLT Evaluable Population. The number and percentage of subjects with DLT will be presented by dose level for dose escalation cohorts. The MTD level will be indicated in the summary.

The MTD will be estimated using isotonic regression (based on the DLTs observed in the DLT evaluable subjects). A MAD will be reported if the DLT rate never reaches $\geq 25\%$. Otherwise, an MTD will be reported. Isotonic regression is a way to estimate the MTD under the assumption that toxicity increases with dose. When using isotonic regression, the first step is to identify the doses where the dose-toxicity monotonicity assumption is violated. The DLT estimate is then adjusted for the violators such that the final estimate of the DLT rate increases with the dose. The target DLT rate is then used to select the MTD. For example, suppose that when the trial is completed, the observed DLT rates [<# subjects who experienced DLT]/[# evaluable subjects] at five dose levels are (0/3, 1/3, 0/3, 4/15, 2/4). In this example the observed DLT rate at Dose Level 2 (i.e., 1/3=33%) is higher than the observed DLT rate at Dose Level 3 (i.e., 0/3=0%). To adjust for this violation, the DLT estimates are replaced with their average, i.e., $(1/3+0/3)/2=1/6$, resulting in the isotonic regression DLT estimates (0/3, 1/6, 1/6, 4/15, 2/4) = (0%, 16.7%, 16.7%, 26.7%, 50%), which monotonically increases with the dose level. Based on this isotonic estimate, assuming that the trial goal is to find the dose with the DLT rate of 30%, Dose Level 4 will be selected as the MTD. If there are no violators of the dose-toxicity monotonicity assumption, isotonic regression directly uses the observed DLT rates as the final estimates for MTD selection. For subjects who undergo intra-subject dose escalation, only DLTs that occur during the DLT period on the subject's initial dose level the assignment will be used for MTD determination.

In the case of dose levels with estimated toxicity of equal distance (tied dose levels) from the target toxicity of 30%, the following approach will be used: among all tied dose levels the highest dose level with target toxicity $\leq 30\%$ will be selected, unless all tied dose levels have estimated toxicity $> 30\%$, in which case the lowest dose level will be selected.

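### SAP 8.1 repairs isotonic violations with a plain average of DLT rates; this is wrong as written when the pooled dose levels differ in size, though it rarely changes the selected MTD

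*SAP*

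**What the plan says.** Protocol 9.2.4 names the estimator without giving an algorithm or weights: "The MTD will be estimated using isotonic regression (based on the DLTs observed in DLT evaluable subjects"). It then sets the selection rule: "the MTD is the dose for which the isotonic estimate of the DLT rate is closest to the target DLT rate of 30" percent. SAP 3.2 gives the same target: "The dose escalation will utilize a mTPI-2 design with target DLT rate of 30% for the MTD".

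SAP 8.1 is the only text that says how a violation of monotonicity is repaired: "To adjust for this violation, the DLT estimates are replaced with their average". The calculation shown is (1/3+0/3)/2 = 1/6. The example behind it has five levels with 0/3, 1/3, 0/3, 4/15 and 2/4, and the two violating levels both hold 3 subjects. Neither document mentions weighting by the number evaluable.

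SAP 3.2 and its Table 2 (Table 5 in the protocol) set cohorts of about 3, a stay decision at observed rates of 25% to 33%, and at most 12 evaluable subjects per level.

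**The concern.** A mean of two rates gives a 3-subject level the same weight as a level two to four times its size. The escalation rules readily produce unequal neighbours. A level that had a DLT, stayed and then cleared holds 6 or more subjects, while the next level can clear at 0/3. That pair is a violation, and the plain mean then pulls the pooled rate below what the subjects show.

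Identifying the MTD or MAD is part of the primary objective. Because the MTD is the dose whose isotonic rate lies nearest 30%, an understated rate at the lower levels moves them away from the target and can tip the choice to a higher dose.

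**Working it through.** **Inputs.** Target 30%; MTD is the level nearest to it; if tied levels are all below 30%, the higher is taken (Protocol 9.2.4, SAP 8.1). Decisions follow SAP Table 2. Four dose levels; cohorts of 3 unless stated.

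**1. The SAP's own example.** Observed 0/3, 1/3, 0/3, 4/15, 2/4.
- Plain: (1/3 + 0/3)/2 = 1/6.
- Weighted: (1 + 0)/(3 + 3) = 1/6.

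Both give 0%, 16.7%, 16.7%, 26.7%, 50% and select Level 4. The printed figures reproduce, but with equal numbers the example cannot tell the two rules apart.

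**2. Unequal numbers.** Adjacent levels with 1/6 and 0/3.
- Plain: (1/6 + 0/3)/2 = 1/12 = 8.3%.
- Weighted: (1 + 0)/(6 + 3) = 1/9 = 11.1%.

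Applied to the nine subjects, 8.3% implies 9 × 1/12 = 0.75 DLTs where 1 was observed.

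**3. A path on which the MTD changes (15 subjects).** Level 1: 1/3 stay, then 1/6 escalate. Level 2: 0/3 escalate. Level 3: 1/3 stay, then 3/6 de-escalate. Stop there.

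| Rule | Levels 1 and 2 | Distance from 30% | Level 3 | Distance from 30% | MTD |
|---|---|---|---|---|---|
| Plain | 8.3% | 21.7 points | 50% | 20.0 points | Level 3 |
| Weighted | 11.1% | 18.9 points | 50% | 20.0 points | Level 2 (tie rule) |

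The same reversal occurs one level up at 0/3, 1/6, 0/3, 3/6 (18 subjects: Level 4 against Level 3). With one cohort of 4 it occurs at 1/6, 0/3, 2/4 (13 subjects).

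**4. What happens if the de-escalation is carried out.** From step 3, three more subjects at Level 2 bring it to 6. Levels 1 and 2 are then equal in size, so the two rules coincide:
- Level 2 at 0/6: both give 8.3% for Levels 1 and 2 and select Level 3.
- Level 2 at 1/6 or 2/6: both select Level 2.
- Level 2 at 3/6: both select Level 1.

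**5. How often.** I listed every data set reachable under Table 2, allowing a stop after any cohort. The middle column counts only data sets in which some final observed rate is at least 25%, so that an MTD rather than a MAD is reported.

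| Escalation subjects, cohorts of 3 | Isotonic rates differ | MTD differs |
|---|---|---|
| up to 12 | 3 of 90 | 0 of 90 |
| up to 15 | 18 of 218 | 1 of 218 |
| up to 18 | 70 of 491 | 4 of 491 |

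The three at 12 are 1/6, 0/3 followed by 1/3, 2/3 or 3/3. The larger totals shift slightly (roughly 480 to 500 at 18) with how the path is continued at the top and bottom levels; the four MTD changes do not. With cohorts of 3 to 4 and up to 18 subjects, the MTD differs in 19 of 3000.

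**The case against.** The strongest reply is that SAP 8.1 names isotonic regression, that the averaging appears inside an example, and that the example is arithmetically correct. A programmer might well run a standard weighted routine. That is fair as a forecast. But the sentence is the only repair rule in either document, and a weighted analysis would depart from it whenever violating levels differ in size.

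The reply also limits the consequence, and this part stands. Observed DLT counts are tabulated by level beside the MTD, escalation itself runs on Table 2, and the RP2D rests on all the data.

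Two stronger readings are tempting, and the documents do not support them. A reader might infer that plain averaging is what lets a dose with a 50% observed DLT rate be named the MTD. The nearest-to-30% rule does that without it: 0/3 then 3/6 has no violation and still selects the 50% level. With correct weighting, 85 of the 491 data sets up to 18 subjects still name a level with an observed rate of 50% or more.

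A reader might also match the 18-subject path to the planned total of 18. That total is about 12 in escalation plus about 6 in the pharmacodynamic cohort, whose subjects do not inform escalation. At the planned 12, in cohorts of 3, no MTD changes.

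**Conclusion.** Wrong as written. The stated rule gives incorrect isotonic DLT rates for many unequal-sized violations; 8.3% against 11.1% is the typical case. The effect on the selected MTD is small: none up to 12 escalation subjects in cohorts of 3, and 4 of roughly 480 to 500 data sets up to 18. In each of those four the plain average picks the higher dose.

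All four end on a de-escalate decision that has not been carried out. SAP section 1 records that enrollment was discontinued prematurely, so such a stopping point is possible. The documents give no DLT counts, so nothing shows that it occurred.

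The counts assume four levels, decisions exactly as in Table 2 and a possible stop after any cohort. They count possible data sets and are not probabilities, because the documents give no dose-toxicity curve.

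**What to change.** In SAP 8.1, replace the averaging sentence with: adjacent dose levels that violate monotonicity are pooled, each receives the total number of DLTs divided by the total number of DLT-evaluable subjects across the pooled levels (pool-adjacent-violators weighted by the number evaluable), and this is repeated until the estimates are non-decreasing. This also settles three or more violating levels, which the present wording leaves open.

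Replace the worked example with one that has unequal numbers and fits this trial, for instance 1/6 and 0/3 pooled to 1/9. The present one uses five levels and a 15-subject level, against four planned levels and a cap of 12. The cost is one sentence and one example, with no effect on trial conduct. The change does not alter how the nearest-to-30% rule treats levels with high observed rates, which is a separate question.

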8.2 Adverse Events

The AE terms on the eCRFs will be mapped to the preferred terms and system organ classes using the Medical Dictionary for Regulatory Activities (MedDRA) version 24.1. Drug-related AEs are defined as AEs with relationship to study treatment being related or possibly related. A worst-case scenario approach will be taken to handle missing data, i.e., AEs with the relationship to study treatment as missing will be counted as drug-related AEs.

An overview summary of AEs will be produced, in which counts and percentages of subjects with any AE, drug-related AEs, DLT, SAEs, drug-related SAEs, fatal AEs, immune related AEs, Grade 3 or 4 AEs, and AEs leading to drug withdrawn, dose not given/held, and dose not completed.

The AE summary tables will use the following algorithms for counting subjects with AEs:

- **Preferred term rows:** each subject is counted once within each unique preferred term at the maximum grade. For example, if a subject has two headaches, the subject is counted only once under the preferred term “Headache”. Subjects experiencing the same AE preferred term several times with different grades will only be counted once with the maximum grade.
- **SOC rows:** each subject is counted only once at the maximum grade at each SOC level although they may have several different preferred term events within the same SOC.
- **Any event row:** each subject with at least one adverse event will be counted only once at the maximum grade no matter how many events they have.

All AEs and drug-related AEs will be summarized by MedDRA system organ class, preferred term and maximum toxicity grade. The non-serious AEs will be summarized by MedDRA system organ class and preferred term. The system organ class and preferred terms will be ordered by descending order of the subject incidence of system organ classes and preferred terms within each system organ class based on all subjects in the analysis population.

The following summary tables will be presented by MedDRA preferred term, in which the preferred terms will be order by descending order of subject incidence of preferred terms based on all subjects in the analysis population.

- Summary of all AEs.
- Summary of drug-related AEs.
- Summary of SAEs.

Listings of all AEs and DLTs will be presented in data listings. Listing of all AEs for the Screen Failures population will be presented in a data listing.

8.3 Clinical Laboratory Evaluation

The clinical laboratory evaluation includes the following:

- Hematology: hemoglobin, hematocrit, platelet count, red blood cell count, white blood cell count with differential.
- Clinical chemistry: blood urea nitrogen, creatinine, glucose, sodium, potassium, calcium, magnesium, phosphorus, total protein, albumin, lactate dehydrogenase, bicarbonate, haptoglobin, ferritin, C reactive protein and liver panel (ALT, AST, total and direct bilirubin, and alkaline phosphatase).
- Coagulation: prothrombin time, international normalized ratio, activated partial thromboplastin time, fibrinogen, and D-dimer.

The clinical laboratory grades will be reported using the CTCAE v5.0. Separate listings will be provided for haematology, clinical chemistry, and coagulation tests. For each listing, baseline value will be specified for each subject.

Clinical laboratory results will be summarized for worst case shift from baseline toxicity grade. Frequencies of maximum observed Grade 0-4 toxicity, as defined by the NCI CTCAE v5.0, will be presented for each laboratory parameter. The determination of the maximum grade post-baseline takes into account both planned and unscheduled assessments. Separate summaries indicating hyper- and hypo- directionality of change will be produced, where appropriate.

8.4 Death

All death records will be presented in a data listing.

8.5 Blood Phenotype and Direct Antiglobulin Test

Blood phenotype and DAT assessment date and result will be presented in a data listing.

8.6 Vital Signs and Pulse Oximetry

Vital signs (blood pressure, heart rate, respiration rate, temperature), body weight and pulse oximetry will be presented in a data listing.

8.7 Cardiac Evaluations

Cardiac evaluation in triplicate measurements will be evaluated at C1D1 and C2D1. Average value of triplicate measurements for heart rate, RR interval, uncorrected QT, QTcB and QTcF will be calculated for each timepoint on C1D1 and C2D1. Change from baseline will be calculated using average value for 1 hour and 4 hours post EOI at C1D1 and Predose at C2D1 minus C1D1 predose average value for each ECG parameter. Cardiac evaluation at screening, C1D1 and C2D1 will be presented in a data listing.

8.8 ECOG Performance Status

Eastern Cooperative Oncology Group (ECOG) performance status scores will be summarized for baseline, and worst-case shift from baseline in a table and presented in a data listing.

9. PHARMACOKINETIC ANALYSES

Pharmacokinetic data analyses will be based on the PK population. If PK analysis assay is performed, serum concentrations for SL-172154 will be summarized and listed, and PK parameters will be summarized and analyzed using appropriate statistical method. If ADA analysis is performed, individual subject ADA data will be summarized by dose level and presented in a data listing.

10. PHARMACODYNAMIC AND BIOMARKER ANALYSES

Pharmacodynamic and biomarker data analyses will be based on the pharmacodynamic population. If the analysis assays are performed, the pharmacodynamic and biomarker results will be summarized by dose level/visit and presented in a data listing.

12.2 List of Figures

ICH Heading	Figure Number	Figure Description	Analysis Population
14.2	14.2.1	Plot of Duration on Treatment and Response	All Treated
	14.2.2	Plot of Maximum Reduction in Sum of Lesion Diameters for Target Lesions	All Treated
	14.2.3	Plot of Maximum Reduction in for Injected and Non-injected Lesions	All Treated

12.3 List of Data Listings

ICH Heading	Listing Number	Listing Description	Analysis Population
16.2		SUBJECT DATA LISTINGS	
16.2.1		Discontinued subjects	
	16.2.1.1	Study Population and Subject Disposition	All Enrolled
	16.2.1.2	Study Treatment Discontinuation	All Treated
16.2.2		Protocol deviations	
	16.2.2.1	Protocol Deviations	All Treated
16.2.4		Demographics	
	16.2.4.1	Demographic and Baseline Characteristics	All Treated
	16.2.4.2	Medical and Surgical History	All Treated
	16.2.4.3	Study Cancer History	All Treated
	16.2.4.4	Prior Anti-Cancer Systemic Treatment	All Treated
	16.2.4.5	Prior Surgery and Radiotherapy Treatment	All Treated
	16.2.4.6	Concomitant Medications	All Treated
	16.2.4.7	Concomitant Procedure	All Treated
16.2.5		Study Drug Exposure	
	16.2.5.1	Study Drug Exposure	All Treated
16.2.6		Individual efficacy response data	
	16.2.6.1	Target Lesions	All Treated
	16.2.6.2	Non-Target Lesions	All Treated
	16.2.6.3	New Lesions	All Treated
	16.2.6.4	Disease Responses by RECIST 1.1	All Treated
	16.2.6.5	Time to Response and Duration of Response Based on RECIST 1.1	All Treated
	16.2.6.6	Progression-Free Survival Based on RECIST 1.1	All Treated
	16.2.6.7	Injected and Non-injected Target Lesions	All Treated
16.2.7		Adverse Event Listings	

ICH Heading	Listing Number	Listing Description	Analysis Population
	16.2.7.1	All Adverse Events	All Treated
	16.2.7.2	Dose Limiting Toxicities	DLT evaluable
	16.2.7.3	Serious Adverse Events	All Treated
	16.2.7.4	Death	All Treated
	16.2.7.5	All Adverse Events for Screen Failure Population	Screen Failure
16.2.8		Individual Laboratory Measurements	
	16.2.8.1	Hematology	All Treated
	16.2.8.2	Clinical Chemistry (including ferritin and haptoglobin)	All Treated
	16.2.8.3	Coagulation	All Treated
16.2.9		Listing of other safety data	
	16.2.9.1	Vital Signs and Pulse Oximetry	All Treated
	16.2.9.2	ECOG Performance Status	All Treated
	16.2.9.3	Cardiac Assessments (ECG)	All Treated
	16.2.9.4	Blood Phenotyping and Direct Antiglobulin Test	All Treated
